## Comparator: Treatment as usual (TAU)

Usual care of BD patients typically consists of pharmacotherapy, psycho-education and selfmanagement interventions (usually with a psychiatric nurse). According to the guidelines (Trimbos Instituut, 2015), these interventions will be or will have been offered to patients prior to participation in the current study. It is expected that a large majority of participants receive some form of pharmacotherapy. Because of the clinical representativeness, we will not restrict TAU in any way. So switching, tapering or augmenting of medication might be part of TAU. We will keep a careful record of this in order to examine and control for possible differences between the two groups. However, frequent psychological treatments, i.e. fortnightly or more, such as (group-based) CBT, will be an exclusion criterion for the current RCT because of practical and methodological reasons. For a detailed description of the biological treatment options that are part of TAU, such as several pharmacotherapeutic options, electroconvulsive therapy, and heliotherapy, we refer to the clinical guidelines "Multidisciplinaire Richtlijn Bipolaire Stoornissen (derde, herziene versie)", pp 121-167 (Trimbos Instituut, 2015). Detailed information for each individual pharmacotherapeutic option can be found on the pharmacotherapeutic compass: https://www.farmacotherapeutischkompas.nl/ (Zorginstituut Nederland, 2017).

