# 6.1.3 Other study parameters

# Baseline parameters

- Age
- Gender
- Ethnicity
- Level of education
- Marital status
- Employment status
- BD type (bipolar I or II)
- Age at onset
- Time since last episode of depression or (hypo)mania
- Number of previous episodes (manic and depressed, reported separately)
- Types and dose of medication being used
- Previous treatment with CBT and/or IP(SR)T (yes/no)
- Suicide attempt (lifetime; yes/no)
- Number of previous hospitalizations due to either manic or depressive episode
- Comorbid psychiatric diagnoses

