## 6.2 Randomisation, blinding and treatment allocation

Randomisation will be performed within the datamanagement system Castor EDC. This will consist of stratified, variable block randomisation with the following stratification variables: Location (site); Gender; Depression (current versus remitted); BD type (I versus II); and number of previous episodes (<12 versus =/> 12). This system also allows for blinded (concealed) allocation such that research assistants on site can be kept blind to condition. MBCT teachers on site will be notified of the allocation to MBCT, allowing them to invite the patient to participate and coordinate further arrangements. As only assessors will be blind to treatment allocation due to the nature of the intervention, no indications for breaking the randomization code are pre-specified. In case of adverse reactions, patients are encouraged to discuss this with their MBCT teacher and responsible clinician.

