## 6.3 Study procedures

Figure 2 provides a flowchart of the study procedures from referral to the final assessment. Patients will be recruited from several specialized, outpatient clinics in the Netherlands; ProPersona, Dimence, and Altrecht, and through the patient association; Vereniging voor Manisch Depressieven en Betrokkenen (VMDB). They will receive a letter from their attending clinicans, informing them about the study with an included information leaflet. This way, patients are free to choose whether to participate in the study, without feeling obligated to their clinicans when asked face-to-face. Interested patients are, after verbal consent is obtained, invited for a screening by telephone to assess global eligibility. Eligible patients will receive more information and a detailed description of the study procedure. After one week, patients will be contacted by telephone to assess whether they are still interested in participation. Patients who are still interested to participate will be invited for intake with a research assistant, where informed consent is obtained. They are thoroughly screened for in- and exclusion criteria with use of the SCID-I and YMRS. Altogether, this will take about 1.5 hours. When patients are still eligible and interested, they are invited for baseline assessment (T0), which consists of several clinician administered measures (IDS-C and FAST), which will take about 20 minutes. After a short pause, participants are asked to conduct five short computer tasks (Stroop, Emotional Stroop Task, Breathing Focus Task, Self Referent Encoding Task, and Attentional Control Scale). This will take about onee hour. However, it is possible for participants to do only the first part of these measures, so they can skip the computer tasks if necessary. Furthermore, participants are asked to fill in several self-report questionnaires at home (STAI, brooding subcale of RRS, CHIME, SCS-SF, MHC-SF, RPA, CTQ, TiC-P, and EQ-5D-5L). After baseline assessment, patients are randomised to one of two groups: TAU or MBCT + TAU. Participants in the intervention group (MBCT + TAU) will receive an eight-week MBCT training, during which they daily have to document mood fluctuations, changes in medication, and major life events in the Life Chart. Furthermore, participants are asked to document adherence and adverse events in a personal diary. Participants in the comparator group (TAU) will receive their treatment as usual, while they daily document in the Life Chart as well. After three months (T1), participants are invited for follow-up assessment, during which the clinician administered questionnaires (YMRS, IDS-C, FAST, SCID-I) and computer tasks will be conducted again. Furthermore, patients are asked to fill out the online self-report questionnaires a second time. More follow-up assessments will take place after 6 months (T2), 9 months (T3), 12 months (T4), and 15 months (T5). During T2, T3, and T4 assessments patients are approached by telephone to assess depressive, manic, and anxiety symptoms, and global functioning over the past three months (IDS-C, YMRS, FAST, and SCID-I to assess manic and depressive symptoms retrospectively). Furthermore, during these assessments patients are asked to fill out the online questionnaires as well. The assessment at 15 months follow-up (T5), will consist of the clinician adminstered meassurements (IDS-C, YMRS, FAST) and the online self-report measurements (STAI, brooding subcale of RRS, CHIME, SCS-SF, MHC-SF, RPA, TiC-P, EQ-5D-5L). Table 1 provides an overview of the assessments. After 15 months of follow-up the study will end, after which participants in the comparator group will be given the opportunity to participate in a MBCT-course as well.

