# 8. STATISTICAL ANALYSIS

Multilevel analysis will be used to account for the cluster-randomized design and therefore the hierarchical structure of the data, with outcome variables at the pre- and postmeasurements at the lowest level, nested within individuals, nested within treatment groups (for the intervention condition), and nested within condition (MCBT + TAU vs TAU). Any baseline parameters that may be inadvertently unequally distributed between the conditions are included as covariates. Multilevel logistic regression will be performed for dichotomous outcomes and multilevel regression analysis for normally distributed continuous outcomes. The clinical outcome data will be analysed and reported according to the CONSORT guidelines, i.e. on intention-to-treat basis. Given the anticipated drop-out, we will also analyze and report on the per-protocol group, and discuss possible differences between the two analysis sets.

Additional analyses will be performed within subgroups with and without a current depressive episode. To account for possible differences between therapy groups, we will add a random group effect. Sensitivity analyses will be conducted with different scenarios of imputed data sets, in case of missing data, to examine the influence of missing data on the pattern of outcomes.

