## 8.1 **Primary study parameter(s)**

The primary analysis is aimed at comparing the effects of MBCT + TAU on depressive symptoms. The primary outcome parameter will be the total scores on the IDS-C. In order to investigate consolidation of treatment effect, we will follow-up participants for another 15 months. We will use a multilevel regression model for repeated measures to analyse differences between baseline, 3 months, 6 months, 9 months, 12 months, and 15 months follow-up measurements.

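### Section 8 chooses covariates by chance baseline imbalance; the five stratification factors should be prespecified instead (modest effect, cheap fix)

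*Protocol*

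**What the plan says.** The only covariate rule is in the general part of Protocol section 8: "Any baseline parameters that may be inadvertently unequally distributed between the conditions are included as covariates". Section 8.1 then describes the primary IDS-C analysis, "We will use a multilevel regression model for repeated measures to analyse differences between baseline, 3 months" and the later visits up to 15 months, and names no covariate.

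Section 6.2 specifies "stratified, variable block randomisation with the following stratification variables: Location (site); Gender; Depression (current versus remitted); BD type (I versus II"), with a fifth factor, fewer than 12 versus 12 or more previous episodes. No section puts these five into a model. Section 8 uses depression status only to define subgroups: "Additional analyses will be performed within subgroups with and without a current depressive episode".

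Section 6.1.3 lists 15 baseline parameters. Gender, BD type and episode count ("Number of previous episodes (manic and depressed, reported separately") are also stratification factors, the last in a different form. Section 8 does not refer to this list.

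Two further statements touch the same edit. Section 5.1 says of medication changes under TAU: "We will keep a careful record of this in order to examine and control for possible differences between the two groups". Section 8 opens with "Multilevel analysis will be used to account for the cluster-randomized design", whereas section 6.3 says "patients are randomised to one of two groups: TAU or MBCT + TAU".

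**The concern.** In a randomised trial, a baseline difference between arms is chance. Choosing covariates by that difference ignores what makes a covariate useful, namely its relation to outcome, and leaves the content of the primary model unknown until allocation and baseline data are seen together. The Protocol is not silent here: it fixes imbalance as the criterion. A cut-off added later would make the rule reproducible, but the covariate set would still depend on the data.

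The rule also fits the design poorly. The factors judged important enough to stratify by are those least likely to look unbalanced on a significance test. At stake are some analytic freedom in the primary result and a little power, not validity.

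**Working it through.** **1. The plan's own figure.** Inputs from section 4.4: effect size 0.5, two-sided alpha 0.05, power 80%, design factor 1 − r² = 0.75 (so r = 0.5), 40% loss. Per arm: 2 × ((1.960 + 0.842)/0.5)² = 62.8; × 0.75 = 47.1, rounded up to 48; 48/(1 − 0.40) = 80. Total 160, as stated, with 160 × 0.6 = 96 expected completers.

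**2. How far the model can vary.** Of the 15 listed parameters, 15 − 3 = 12 are not stratified. Treat these as independent, with 80 per arm. A test at level a selects 12a on average, and at least one with probability 1 − (1 − a)^12. For the absolute standardised mean difference (SMD), the standard error is √(2/80) = 0.158, so P(SMD > 0.10) = P(|z| > 0.63) = 0.53.

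| Reading of the rule | Expected number selected of 12 | At least one of the five stratification factors selected (simulated) |
|---|---|---|
| p < 0.05 | 0.6 | 0-1.5% |
| p < 0.10 | 1.2 | 0.4-5% |
| p < 0.20 | 2.4 | 3-19% |
| SMD > 0.10 | 12 × 0.53 ≈ 6.3 | 71-92% |
| SMD > 0.20 | 12 × 0.206 ≈ 2.5 | 6-28% |
| SMD > 0.25 | 12 × 0.114 ≈ 1.4 | 1-10% |

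The chance of at least one of the 12 is 46%, 72% and 93% at the three p cut-offs. The last column treats all five factors as candidates and spans four assumed block-size sets and three assumed prevalence sets. Stratification tends to balance the factors but does not guarantee it: 3 sites × 2⁴ = 48 strata for 160 patients is about 3.3 per stratum.

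**3. Effect on the result.** Seven readings were compared: no extra covariate, plus the six cut-offs above. From section 4.4: 160 patients, sites of 60/50/50, 40% loss (taken as random), r = 0.5, d = 0.5. Assumed: prevalences, block sizes, and factors adding 2%, 5% or 10% of variance beyond baseline.

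| Model | Verdict differs between readings (d = 0.5) | Best of seven significant (no effect) |
|---|---|---|
| Six visits, arms equal at baseline | 4-6% | 5.0-5.7% |
| Six visits, arms free at baseline | 2-4% | 4.9-5.5% |
| T1 only, ANCOVA on baseline IDS-C | 12-16% | 6.6-7.9% |

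In the T1 model, type I error under any single reading was 4.0-5.1%. The estimate spread across readings by 0.06-0.09 SD on average. The six-visit model used a random intercept and no therapy-group effect. Adding an assumed therapy-group ICC of 0.05 to the T1 model gave 12.5% and 6.6%. Monte Carlo standard errors are 0.2-1.0 points.

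**4. Power when the five factors are prespecified**, against baseline only (factors adding 2/5/10%; other candidates unrelated to outcome).

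| Model | Baseline only | Five factors |
|---|---|---|
| Six visits, arms equal at baseline | 81.4/80.8/79.5% | 82.2/83.7/84.4% |
| Six visits, arms free at baseline | 74.6/73.4/72.8% | 74.6/74.4/74.2% |
| T1 only | 78.8/79.0/79.6% | 78.4/79.9/83.2% |

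The change is about 0 to +5 points over six visits. At T1 it is about −1 to +4 once runs with prognostic other candidates (R² 10%) are included: 79.2/80.2/78.3% against 78.5/80.2/82.3%.

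**The case against.** The best defence is that the measure, cut-off and candidate list are matters a statistical analysis plan normally settles, and that plan is not at hand. This stands: their absence is no fault of the Protocol, and nothing shows that a reading would be picked after the results are seen. The rule itself survives the objection, because imbalance remains the criterion under any cut-off.

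It is also fair that the T1 figures do not come from the model in section 8.1, and that disagreement among any of seven readings is a worst case. In a simpler T1 check with 12 non-prognostic candidates, some pair of readings disagreed in 10.5% of trials but the average pair in 4.1%. Without SMD > 0.10 the 10.5% fell to 6.7%, and the best-reading error fell from 6.6% to 6.0%.

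Stronger readings that a reader might infer, and why they fail:

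- Site and depression status can never be selected, because the section 6.1.3 list omits them. Section 8 makes no link to that list.
- Section 5.1 adds a second covariate rule to the primary model. It names no outcome or model and may describe a supplementary analysis.
- The rule cuts power from 79% to 66-67%. That calculation lets baseline IDS-C enter only when it is unbalanced, whereas section 8.1 already has baseline in the model.
- The label in section 8 means that clustering is mishandled. Section 8 already adds a random therapy-group effect, so the label is a wording error.

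**Conclusion.** The point holds as a modest one that should be fixed. Section 8 lets chance imbalance decide what enters the primary model and leaves out the factors on which allocation was based. Selection uses allocation and baseline data but not outcomes, so the treatment estimate is not biased, and type I error under one fixed reading stays near 5%. In the planned six-visit model the freedom amounts to a changed verdict in about 2-6% of trials and a best-reading type I error of about 5-5.7%. The T1 figures of 12-16% and 6.6-7.9% are an upper case.

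These sizes rest on assumed prevalences, block sizes, R² values, independent candidates and random loss. Only continuous outcomes were simulated, so nothing here shows that five extra terms are harmless in the multilevel logistic models.

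**What to change.** Replace the imbalance sentence in section 8 with a statement that site, gender, depression status (current or remitted), BD type and previous episodes (<12 or ≥12) enter the primary IDS-C model and the continuous secondary models as prespecified fixed effects. Drop depression status within its own subgroups. Keep baseline IDS-C in the model as section 8.1 plans.

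Keep imbalance-driven adjustment only as a labelled sensitivity analysis. Treat any adjustment for medication changes after randomisation (section 5.1) the same way, since MBCT may itself influence such changes.

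The cost is 2 degrees of freedom for three sites plus 4 for the binary factors, 6 in all, against about 96 expected completers. All five factors are needed for randomisation anyway, so no new data are collected and N stays 160. The worst simulated case is a loss of about 1 point of power, in the T1 model when the factors add only 2% of variance.

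As a separate wording correction, section 8 should describe the design as individually randomised and stratified, with therapy-group clustering in the MBCT arm, and treat condition as a fixed effect, not a nesting level.

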## 4.4 Sample size calculation

Sample size calculation is based on the estimated change in depressive symptoms form pre- to posttreatment. As we aim to include patients with all levels of depressive symptoms, we based our calculation on a previous study conducted at the Radboudumc Centre for Mindfulness (van Aalderen et al., 2012). In this study, levels of depression as assessed with the Inventory of depressive symptomatology – self-rated (IDS-SR) decreased in the MBCT+TAU group (n = 102) from 14.9 ( $\pm$  9.2) to 10.3 ( $\pm$  7.8) whereas the TAU group (n = 103) showed no change in depression levels (pretreatment: M = 16.2 ( $\pm$  9.4) and posttreatment: M = 16.2 ( $\pm$  9.8). This corresponded to an effect size of 0.5 for reduction of depressive symptoms in patients with recurrent (unipolar) depression (remitted n = 124, currently depressed n = 58). Based on a two-sided test with an alpha of 0.05 and a power of 80%, with an estimated effect size of 0.5, including a design factor of 1 – r2 (0.75), and taking account of a conservative estimate of 40% loss to follow-up, we intend to recruit N = 160 patients (80 per group).

We anticipate that about 25% of the population will have to be excluded due to (hypo)manic symptoms (when exceeding the maximum on the Young Mania Rating Scale) or other exclusion criteria. We further expect about 25% of the eligible patients to be interested in the study.

Approximately 690 BD patients are treated in ProPersona, with 518 (75%) meeting the inclusion criteria, of whom 130 (25%) would probably be interested to participate. The intended number of participants (n = 60) falls comfortably within this estimate. The number of BD patients treated in Dimence is about 900, with 675 (75%) meeting the inclusion criteria, of whom 169 (25%) would probably be interested to participate. Again, the intended number of participants (n = 50) falls well within this estimate. Approximately 650 BD patient are treated in Altrecht, with 100-150 new patients per year. About 487 (75%) of BD patients would be meeting the inclusion criteria, of whom 122 (25%) would probably be interested. The intended number of participants (n = 50) therefore seems feasible. Moreover, we will recruit patients through the patient association Vereniging voor Manisch Depressieven en Betrokkenen (VMDB) and the psychiatry department of the Canisius Wilhelmina

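### Separate analyses by current depression, with no between-subgroup contrast, cannot show whether the MBCT effect depends on depression status

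*Protocol*

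**What the plan says.** The general part of protocol section 8 (Statistical analysis) states: "Additional analyses will be performed within subgroups with and without a current depressive episode". Neither there nor in sections 8.1 to 8.3 is there an interaction term or any other comparison of the treatment effect between these two subgroups.

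Section 6.2 makes the same characteristic a stratification variable: "Depression (current versus remitted". The only moderation analysis, in section 8.3, concerns childhood traumatic events.

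The sample size in section 4.4 is set for the overall comparison only. It aims for 80% power at the two-sided 5% level "with an estimated effect size of 0.5", applies a factor of 0.75 for the baseline correlation, allows for 40% dropout, and arrives at 80 patients in each arm. The protocol gives no expected share of currently depressed patients for this trial. The nearest figure is the composition of the cited unipolar study: "remitted n = 124, currently depressed n = 58".

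**The concern.** Whether MBCT works differently in depressed and remitted patients is a question about the difference between two effects. Separate analyses give two estimates and two p-values but no estimate of that difference, and no measure of its uncertainty.

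Readers will set the two results side by side. Section 1 faults earlier studies for enrolling mostly remitted patients, section 4.4 aims for patients at every level of depressive symptoms, and section 6.2 stratifies on status. Each subgroup is much smaller than the sample for which power was planned. One significant and one non-significant result is therefore a common outcome even when the effects are identical, and it is easily misread as a difference in benefit.

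**Working it through.** **Inputs.** From section 4.4: two-sided alpha 0.05, power 80%, d = 0.5 (SD = 1), design factor 0.75 (residual SD = √0.75 = 0.866), 40% loss, 80 per arm. Assumption: the share currently depressed is 58/182 = 31.9%, as in the cited unipolar study. Shares of 25%, 40% and 50% were also tried.

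**The protocol's own figure.** n per arm = 2(1.960 + 0.842)²/0.5² = 62.8, so 63. Then 63 × 0.75 = 47.25, rounded up to 48, and 48/0.6 = 80 per arm, N = 160. The t-based n of 64 gives the same result: 64 × 0.75 = 48. The sample size is reproduced.

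**Subgroup power.** Of 48 evaluable per arm, 48 × 124/182 = 32.7 are remitted and 48 × 58/182 = 15.3 depressed. Two-sample t power at d = 0.5/0.866 is 0.633 (remitted) and 0.339 (depressed).

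**Outcomes when the true effect is the same in both.** The subgroups are independent, so:

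- remitted only: 0.633 × 0.661 = 0.418
- depressed only: 0.339 × 0.367 = 0.124
- exactly one: 0.418 + 0.124 = 0.543 before rounding of the parts
- both: 0.633 × 0.339 = 0.215
- neither: 0.367 × 0.661 = 0.243

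**Range over the unknown split and loss** (t-based, factor 0.75):

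| Evaluable | Share depressed | Power depressed | Power remitted | Exactly one significant | Of which remitted only |
|---|---|---|---|---|---|
| 96 | 25% | 27% | 68% | 58% | 49% |
| 96 | 31.9% | 34% | 63% | 54% | 42% |
| 96 | 40% | 41% | 58% | 51% | 34% |
| 96 | 50% | 50% | 50% | 50% | 25% |
| 160 | 25% | 43% | 88% | 55% | 50% |
| 160 | 31.9% | 52% | 85% | 48% | 40% |
| 160 | 40% | 62% | 80% | 43% | 30% |
| 160 | 50% | 72% | 72% | 40% | 20% |

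The normal approximation gives 39% in the last row and 58% in the first. Without the 0.75 factor it gives 48% to 58%. The overall range is therefore about 39% to 58%.

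**Simulation.** In 20,000 runs per scenario with identical effects, exactly one subgroup was significant in 55% (96 evaluable, borrowed split), 50% (96, 50/50), 49% (160, borrowed split) and 40% (160, 50/50). In the same runs the interaction test falsely declared a difference in 4.9% to 5.1%.

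**Precision of the interaction.** SE = 0.866 × √(2/32.7 + 2/15.3) = 0.379, so the 95% half-width is 1.96 × 0.379 = 0.74 SD. Power for a true difference of 0.5 between the subgroup effects is Φ(0.5/0.379 − 1.96) = 26%. With 160 evaluable and a 50/50 split, SE = 0.866 × √(2/40 + 2/40) = 0.274, and power is 45%.

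**The case against.** The strongest reply is that the misuse is not in the document. A reader might infer that the investigators will claim a differential effect because one p-value falls below 0.05 and the other does not. The protocol does not say so. The analyses are labelled additional, section 2 sets no objective on depression status (its only subgroup contrast concerns the number of previous episodes), and separate estimates can be descriptive. This stands, and it limits the point to the form of the planned analysis.

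A second reply is that an SAP, which was not available here, may add the interaction. That is possible. But section 8 does choose a form of analysis, and section 8.3 names moderation analysis for another characteristic, so the sentence would need to be brought into line in any case.

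A third is that the figures depend on a borrowed split, the cautious 40% loss and a single comparison at T1. The planned multilevel repeated-measures model can use partial data and includes a therapy-group effect, so the exact percentages would shift. The general result still holds across the range tried: even with no loss and equal subgroups, discordance is about 39%.

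Finally, stratification balances the arms within each subgroup but does not make the interaction precise. It needs no new data, yet its half-width of 0.74 SD exceeds the whole planned effect of 0.5.

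**Conclusion.** The point holds in a limited form. The planned output cannot show whether the MBCT effect differs by depression status. With an identical effect of d = 0.5 in both subgroups, it would give discordant significance in about 54% of trials at the planned evaluable size and borrowed split, and in about 39% to 58% over the scenarios tried. These figures assume one baseline-adjusted comparison at T1 and equal arms within subgroups.

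A reader might go further and infer that a finding of benefit in remitted patients only is the expected result. The protocol does not support that. Under the borrowed split with 96 evaluable, this pattern has a probability of about 42%: more likely than any other single pattern, but still absent in most trials. At 50/50 it is no more likely than the reverse (20% to 25% each). The protocol states no split for this population.

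The primary analysis, sample size and data collection are not affected.

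**What to change.** Replace the sentence in section 8. In the full primary model, on all patients, add treatment by baseline depression status (current versus remitted, as stratified) and estimate this contrast at T1. Report the interaction estimate with its 95% confidence interval. Take the subgroup effects, with intervals, from the same model and label them descriptive. State that no claim of a differential effect will be made from within-subgroup p-values.

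State the limit in the same place: power is only about 26% to 45% for a true difference of 0.5, so the interaction is to be read as an estimate, and a non-significant result is not evidence of equal effects.

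The cost is analysis wording, plus alignment of the SAP if it says otherwise. No patients, visits or measurements are added.
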